## 7.7. EXAMINATION OF SUBGROUPS

Subgroup analyses will be conducted as stated in [Sections 16.1.5](#). It should be noted that the study was not designed to detect treatment differences with high statistical power within subgroups.

Document: \[REDACTED]\net\enterprise\Apps\sasdata\SASb\SAS\Atea\_Pharmaceuticals\AT-527\SAZ\A63631\Biostatistics\Documentation\SAP\AT-03A-001\_V1.0\_COVID\_SAP\_PA7.doc  
Author: \[REDACTED] Version Number: V1.0  
Template No.: CS\_TP\_BS016 Revision 6 Version Date: 15Apr2021  
Effective Date: 02Dec2019 Reference: CS\_WI\_BS005

Copyright © 2009, 2010, 2012, 2016, 2018, 2019 \[REDACTED] All rights reserved. The contents of this document are confidential and proprietary to \[REDACTED] Holdings Inc. and its subsidiaries. Unauthorized use, disclosure or reproduction is strictly prohibited.

The subgroups are:

- Age (years) at informed consent (< 70 and  $\geq$  70);
- Gender (male and female);
- Geographic region (See [Section 7.6](#));
- Obesity ( $\text{BMI} > 30 \text{ kg/m}^2$  and  $\text{BMI} \leq 30 \text{ kg/m}^2$ ) at screening;
- Hypertension co-morbidity at screening (Systolic Blood Pressure (SBP)  $> 140$  and/or Diastolic Blood Pressure (DBP)  $> 90$ ) (yes and no);
- Diabetes co-morbidity at study entry (yes or no);
- Asthma co-morbidity at study entry (yes and no);
- Number of high-risk factors (1,  $>1$ ) (Obesity at screening, hypertension co-morbidity at screening, diabetes and asthma co-morbidities at study entry);
- Number of comorbidities (1,  $>1$ ) from Medical History CRF page (including alcohol and drug abuse);
- Time since start of COVID-19 symptoms (< median and  $\geq$  median) (ITT analysis set);
- Time since initial COVID-19 diagnosis to screening (< median and  $\geq$  median) (ITT analysis set);
- Baseline quantitative SARS-CoV-2 (< median and  $\geq$  median) (mITT analysis set).

If data are too sparse for one subgroup (i.e., less than 5% of subjects in the subgroup), neither descriptive statistics nor statistical inferences will be provided for that subgroup, as well as for its complementary subgroup. For example, if only 5% of subjects have obesity, no subgroup analysis will be provided for the subjects with or without obesity.

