4.2. Inclusion Criteria

1. Willing and able to provide informed consent.
2. Male or female subjects ≥ 18 years of age.
3. Subject is hospitalized or in a hospital-affiliated confinement facility for which the principal investigator is credentialed and study staff have access to study participants and their data.
4. Subject must be diagnosed with COVID-19 (SARS-CoV-2 positive) by a standard assay or equivalent testing. *Note: SARS-CoV-2 infection will be confirmed with an FDA EUA-approved assay.*
5. Moderate disease defined by the following:
 - Symptoms of COVID-19, with initial symptom onset within 5 days prior to Screening:
 - At least 1 of the following: fever ($> 38.3^{\circ}\text{C}$), cough, sore throat, fatigue/malaise, headache, muscle pain, or more significant lower respiratory symptoms including dyspnea (at rest or with exertion)
 - Clinical signs indicative of COVID-19 (as above), with:
 - $\text{SpO}_2 \geq 93\%$ on room air or requires $\leq 2\text{L}/\text{min}$ oxygen by nasal cannula or mask to maintain $\text{SpO}_2 \geq 93\%$
6. Subjects must also have at least one of the following known risk factors for poor outcomes: obesity ($\text{BMI} > 30$), hypertension, diabetes or asthma.
7. QTcF interval ≤ 450 ms for males and ≤ 460 ms for females at Screening.
8. Females of childbearing potential must agree to use protocol specified methods of contraception as described in [Section 5.9](#).
9. Females of childbearing potential must have a negative pregnancy test at Screening.
10. Subject must be able to take oral tablet medications.

Protocol Number: AT-03A-001

11. Subject is, in the opinion of the investigator, willing and able to comply with the study drug regimen and all other study requirements.

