5.8. Prior and Concomitant Medication

Continuation of subject's maintenance medications is allowed - e.g. medications for treatment of hypertension, high cholesterol, anti-coagulation prophylaxis, asthma, diabetes, HIV, musculoskeletal disorders, cardiac arrhythmias, anxiety disorders, medication-controlled psychosis, etc. Concomitant medications will be documented in the study case records. If there are questions regarding concomitant medications for individual subjects, the Investigator or a site team member should contact their CRO site monitor.

As convalescent plasma may be considered standard of care in some regions, it's concomitant use is allowed in this study.

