### 16.1.5. SUPPLEMENTARY ANALYSES FOR PRIMARY EFFICACY ENDPOINT

The following supplementary analyses will be performed for the primary efficacy endpoint:

- For each subgroup defined in [Section 7.7](#), number and proportion of subjects with and without PRI during the study of 14 days will be provided by treatment group.
- The primary analysis of the primary efficacy endpoint will be repeated to analyze the proportion of subjects

Document: \\[REDACTED]\net\enterprise\Apps\sasdata\SASb\SAS\Atea\_Pharmaceuticals\AT-527\{SZA63631\}\Biostatistics\Documentation\SAPI\AT-03A-001\_V1.0\_COVID

Author: [REDACTED] Version Number: - V1.0  
Version Date: 15Apr2021

Template No.: CS\_TP\_BS016 Revision 6

Reference: CS\_WI\_BS005

Effective Date: 02Dec2019

Copyright © 2009, 2010, 2012, 2016, 2018, 2019 [REDACTED] All rights reserved. The contents of this document are confidential and proprietary to [REDACTED] Holdings Inc. and its subsidiaries. Unauthorized use, disclosure or reproduction is strictly prohibited.

with PRI on or before Days 10, 21, 28 and 63, respectively, instead of the 14-day primary study period.

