- Using 65 for age group instead of 70. (Table 14.1.4.1, 14.2.1.3, 14.2.2.3, 14.2.3.3, 14.2.4.3)
- Hypertension co morbidities will use MHTERM=Hypertension instead of baseline diastolic and systolic values. (Tables 14.1.4.1 and 14.1.4.2)
- Updated derivation for symptom resolution: Time to symptom resolution (days) = (Latest post-baseline assessment symptom end date – Date of randomization) +1. (Tables 14.2.4.X)
- We clarified in footnote that we are using both TaqPath and COBAS tests results for mITT population. (See footnotes in tables)
- For titer data we updated AVAL to 1.2 and 0.45 respectively for results <1.5 and <0.75 in summaries:
  - o It is as per Atea's virologist request and the logic is (Tables 14.2.5.5 and 14.2.4.6):
    - For "<1.5", we should use 15.8, i.e.  $[10^{1.5}]/2$ , as the untransformed value which is 1.2 on log10 scale.
    - For "<0.75", we'll use 2.8, i.e  $[10^{0.75}]/2$ , as the untransformed value which is 0.45 on the log10 scale.
- Time to Sustained Non-detectable SARS-CoV-2 will be displayed by method (COBAS/ TaqPath). (Table 14.2.5.4)
- Level of SARS-CoV-2 Infectious Titer analysis will use the same approach as for the "Time to sustained non-detectable SARS-CoV-2 (mITT)" output, we will be providing estimates of proportion of subjects with undetectable/negative results, using K-M estimates. (Table 14.2.5.6)
- For all tests except ANCOVA, the 2-sided pvalue will be displayed.
- Childbearing potential and HgbA1c are not included in Demographics and baseline characteristics table. (Tables 14.1.4.1 and 14.1.4.2)
- ANCOVA analysis: Present the Change-from-Baseline LSM (SE) for each treatment group. (Table 14.2.5.1)
- Subject level deviations and site level deviations are listed separately.
- Information present in the SAP which are not presented:
  - o Subjects with screen failure.
  - o Inclusion and exclusion summary.
  - o Deviation summary.
  - o Medical History summary.
  - o Disease history summary.
  - o Medication summary.
  - o Exposure summary.

Form No: CS\_FM\_BS006 Revision 8  
Effective Date: 15Jan2020

Reference: CS\_WI\_BS005, CS\_WI\_BS013

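### SAP 7.7 classifies hypertension by screening blood pressure, so treated hypertensives can be misclassed and an eligible subject can have a risk-factor count of 0, which has no category

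*SAP*

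**What the plan says.** SAP Section 7.7 lists the hypertension subgroup as "Hypertension co-morbidity at screening (Systolic Blood Pressure (SBP" and completes it with cut-offs of SBP above 140 and/or DBP above 90, classed yes or no. Neither history nor treatment enters. SAP Section 10 uses the same rule for the baseline table. Further down the Section 7.7 list, the number of high-risk factors is split into 1 and >1 and is derived from "Obesity at screening, hypertension co-morbidity at screening, diabetes and asthma co-morbidities at study entry". For each of these subgroups, SAP Section 16.1.5 says that "number and proportion of subjects with and without PRI during the study of 14 days will be provided by treatment group".

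Protocol Section 4.2, criterion 6, reads "Subjects must also have at least one of the following known risk factors for poor outcomes" and then names obesity, hypertension, diabetes and asthma. Only obesity has a numerical limit (BMI above 30). Protocol Section 5.8 adds: "Continuation of subject's maintenance medications is allowed - e.g. medications for treatment of hypertension".

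The Changes to Planned Statistical Analyses Form of 16 March 2022 states "Hypertension co morbidities will use MHTERM=Hypertension instead of baseline diastolic and systolic values. (Tables 14.1.4.1 and 14.1.4.2"). The item just before it states "Using 65 for age group instead of 70. (Table 14.1.4.1, 14.2.1.3, 14.2.2.3, 14.2.3.3, 14.2.4.3"). The same form drops the supplementary PRI analyses apart from those on subgroups, limits Part B to listings, and says that the SAP itself will stay as it is.

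**The concern.** The two levels of the risk-factor count make sense only if every enrolled subject has at least one factor. Criterion 6 guarantees that for correctly enrolled subjects. The SAP derivation does not, because it replaces the factor that admitted the subject with a blood-pressure reading that treatment may have normalised.

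Three things follow if Section 7.7 is programmed as written. The hypertension subgroup can be wrong in both directions. The risk-factor split is not exhaustive, so its levels need not add up to the ITT total. And the baseline tables, once switched to medical history, can show a different number of hypertensive subjects from the subgroup tables in the same report.

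**Working it through.** This point concerns a variable definition. It depends on no sample size, power or alpha in the plan, so there is no stated figure to reproduce.

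**Step 1: compare the two definitions.** Criterion 6 gives obesity, hypertension (no threshold), diabetes, asthma. Section 7.7 gives obesity, screening pressure above 140 and/or 90, diabetes, asthma. The obesity cut-off (BMI above 30) is the same in both. Hypertension is the one factor for which the SAP imposes a reading that the criterion does not ask for.

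**Step 2: enumerate the eligible patterns.** Four yes/no factors with at least one present give 2^4 − 1 = 15 patterns. Each can occur with screening pressure raised or not raised, giving 30 cases. Compare

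- count by criterion 6 = obesity + hypertension + diabetes + asthma
- count by Section 7.7 = obesity + raised screening pressure + diabetes + asthma

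| Hypertensive | Screening pressure | Other factors | Level by criterion 6 | Level by Section 7.7 |
|---|---|---|---|---|
| yes | at or below 140/90 | none | 1 | 0 (no category) |
| yes | at or below 140/90 | one | >1 | 1 |
| yes | at or below 140/90 | two or three | >1 | >1 |
| no | raised | one | 1 | >1 |
| no | raised | two or three | >1 | >1 |

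All remaining cases agree. Because obesity, diabetes or asthma can each be the single other factor, the second and fourth rows stand for three cases each. So 7 of the 30 cases change level: 1 from 1 to 0, 3 from >1 to 1, and 3 from 1 to >1. These are counts of patterns, not of subjects.

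**Step 3: how many subjects could score 0?** The documents do not say. For illustration, take the 81 subjects randomized in Part A (Protocol Section 3.2) and put

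N0 = 81 × p × q

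where p is the share whose only factor is hypertension and q is the share of those at or below 140/90 at screening. Both are assumptions: p from 10% to 40%, q from 30% to 70%.

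- low: 81 × 0.10 × 0.30 = 2.4
- middle: 81 × 0.20 × 0.50 = 8.1
- high: 81 × 0.40 × 0.70 = 22.7

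The range of about 2 to 23 shows only how much the answer depends on p and q. It is not an estimate for this trial.

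**Step 4: does the 2022 form already cure it?** The form adopts the medical-history term, which is the right variable, but ties it to two tables. The adjacent age item names 14.1.4.1 and four tables numbered 14.2.x.3. Apart from baseline characteristics, the SAP groups subjects by age only in Section 7.7, so the 14.2.x.3 tables are most naturally read as subgroup tables. This is an inference, since the table titles are not in the documents. On that reading the hypertension item does not reach them, and Section 7.7 still governs.

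**Step 5: check the repair.** If hypertension is taken from medical history, and each subject admitted on hypertension has it recorded there, the count is at least 1 in all 15 patterns. The levels 1 and >1 are then exhaustive.

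**The case against.** The best reply is that the sponsor has already made this correction and that reading the bracketed table numbers as a limit argues from silence. Those lists do not look reliably complete. The age item cites 14.1.4.1 but not 14.1.4.2, although another item on the form treats both as demographic and baseline tables. The output templates are not available, so nobody can see from the documents which variable feeds the subgroup tables. This stands as far as it goes: a reader might infer that the report will contain two conflicting hypertension counts, and the documents show only that it could. It does not remove the point, because nothing in the form extends the change and the SAP text is left in force.

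A second reply is that criterion 6 does not define hypertension by history or treatment either, and that the SAP states its own rule openly. That is also fair, and it rules out calling the subgroup invalid. It does not help the risk-factor count, whose two levels presuppose that eligibility and derivation agree.

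A third reply is that little depends on this variable. That is correct. Section 16.1.5 asks only for numbers and proportions by arm, and Section 7.7 itself disclaims high power within subgroups. The protocol's rationale for Amendment 8 concedes that PRI events are too few for a meaningful clinical comparison, and Part B is only listed. No primary, key secondary or multiplicity result uses the variable.

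**Conclusion.** The point holds as a minor defect in a stated rule. As written, Section 7.7 can misclass hypertension in both directions and can leave an eligible subject with a count of 0 and no category. The 2022 form does not, on its wording, carry its own correction to the subgroup tables or the count.

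Two stronger readings should be resisted. One is that subjects have in fact dropped out of the risk-factor split. No document reports how many had hypertension as their only factor or what their screening pressures were. The other is that the affected share must be sizeable because antihypertensives are allowed. Section 5.8 merely permits maintenance medication, with hypertension as one example among many, and says nothing about how often it was used or how well pressure was controlled.

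The conclusion rests on two readings: that the phrase reused in the count carries the blood-pressure definition given earlier in the same list, and that the 14.2.x.3 tables are subgroup tables. If the sponsor intended the medical-history term throughout, only the missing statement and the handling of a zero count remain.

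**What to change.** State in the changes form, or in Section 7.7, that the rule "Hypertension co morbidities will use MHTERM=Hypertension instead of baseline diastolic and systolic values" applies to every table, including the subgroup tables and the number of high-risk factors. Build the count from that variable together with obesity, diabetes and asthma. Medical history is the documented source to use: the protocol collects risk factors with it, and the form has already adopted the term. A separate eligibility field for hypertension is not described in either document.

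Add one rule for any subject who still scores 0, for example because the term was not recorded. Show that subject in a 0 category, or report an eligibility deviation.

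The cost is a sentence or two of wording, one derivation using a variable already programmed for the baseline tables, and a rerun of any subgroup table that used blood pressure.

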## 7.8. SOFTWARE VERSION

All analyses will be conducted using SAS version 9.4.

Document: \[REDACTED]\net\enterprise\Apps\sasdata\SASb\SAS\Atea\_Pharmaceuticals\AT-527\SA63631\Biostatistics\Documentation\SAP\AT-03A-001\_V1.0\_COVID\_SAP\_PA7.doc  
Author: [REDACTED] Version Number: V1.0  
Template No.: CS\_TP\_BS016 Revision 6 Reference: CS\_WI\_BS005  
Effective Date: 02Dec2019 Version Date: 15Apr2021

Copyright © 2009, 2010, 2012, 2016, 2018, 2019 [REDACTED] All rights reserved. The contents of this document are confidential and proprietary to [REDACTED] Holdings Inc. and its subsidiaries. Unauthorized use, disclosure or reproduction is strictly prohibited.

## 8. OUTPUT PRESENTATIONS

[APPENDIX 2](#) shows conventions for presentation of data in outputs.

The templates provided with this SAP describe the presentations for this study and therefore, the format and content of the summary tables, figures, and listings to be provided by [REDACTED] Biostatistics.

## 9. DISPOSITION AND WITHDRAWALS

All subjects who provide informed consent will be accounted for in this study.

### 9.1. DISPOSITION

Number of subjects screened will be presented overall for the SCRN analysis set. Number and percentage of subjects with screen failure and reason for screen failure will also be presented overall based on the SCRN analysis set. Number of subjects randomized will be presented overall and by treatment group for the SCRN analysis set.

Number and percentages of subjects treated, who completed/discontinued early from treatment (including reason for withdrawal), and who completed/discontinued early from the study (including reason for withdrawal) will be provided overall and by treatment group based on the ITT analysis set.

Similarly, number of subjects included and excluded from each analysis set (including reason for exclusion) will be summarized overall and by treatment group based on the ITT analysis set. A listing showing inclusion and exclusion of each subject from each analysis set, including reason for exclusion, will be provided.

### 9.2. PROTOCOL DEVIATIONS

All protocol deviations (critical, major, and minor) will be recorded in the clinical trial management system (CTMS) protocol deviations log for the duration of the study (refer to the Protocol Deviations Management Plan for the definition of critical, major, and minor protocol deviations). Site-level identified protocol deviations will be replicated for all subjects ongoing in the study at the site at the time of the protocol deviation and presented in the summary outputs as subject-level protocol deviation unless otherwise indicated at the deviation review meeting before DBL.

Document: \[REDACTED]\net\enterprise\Apps\sasdata\SASb\SAS\Atea\_Pharmaceuticals\AT-527\SA63631\Biostatistics\Documentation\SAP\AT-03A-001\_V1.0\_COVID\_SAP\_PA7.doc  
Author: [REDACTED] Version Number: V1.0  
Template No.: CS\_TP\_BS016 Revision 6 Version Date: 15Apr2021  
Effective Date: 02Dec2019 Reference: CS\_WI\_BS005

Copyright © 2009, 2010, 2012, 2016, 2018, 2019 [REDACTED] All rights reserved. The contents of this document are confidential and proprietary to [REDACTED] Holdings Inc. and its subsidiaries. Unauthorized use, disclosure or reproduction is strictly prohibited.

Number and percentage of subject with critical and major protocol deviations will be provided overall and by treatment group based on the ITT analysis set for each category of protocol deviations specified in the Protocol Deviations Management Plan.

A listing of protocol deviations identified by the study team (critical, major, and minor) will be provided.

## 10. DEMOGRAPHIC AND OTHER BASELINE CHARACTERISTICS

The following demographic and other baseline characteristics will be reported for this study:

- Age (years) – calculated relative to date of consent, as continuous and categorical (<70 and  $\geq$ 70);
- Gender (male or female);
- Geographic region;
- Childbearing potential for female subjects only (yes or no; and reasons if not of childbearing potential);
- Race (American Indian or Alaska Native, Asian, Black or African American, Native Hawaiian or Other Pacific Islanders, White, Not Reported, Unknown);
- Ethnicity (Hispanic or Latino, Not Hispanic or Latino, Not Reported, Unknown);
- Weight (kg);
- Body Mass Index (BMI) ( $\text{kg}/\text{m}^2$ );
- Obesity ( $\text{BMI} > 30 \text{ kg}/\text{m}^2$  and  $\text{BMI} \leq 30 \text{ kg}/\text{m}^2$ );
- Hemoglobin A1c (mmol/mol);
- Hypertension co-morbidity at screening (Systolic Blood Pressure (SBP)  $> 140$  and/or Diastolic Blood Pressure (DBP)  $> 90$ ) (yes and no);
- Quantitative SARS-CoV-2 based on central lab;
- Clinical Status Score;
- Immunoglobulin G (IgG) (if data available);

Document: \\[REDACTED]\net\enterprise\Apps\sasdata\SASb\SAS\Atea\_Pharmaceuticals\AT-527\SAZ\A63631\Biostatistics\Documentation\SAP\AT-03A-001\V1.0\_COVID\_SAP\_PA7.doc  
Author: [REDACTED] Version Number: [REDACTED]

Author: [REDACTED] Version Number: V1.0  
Template No.: GS\_TB\_RS016 Revision 6 Version Date: 15April2021  
Reference: GS\_WL\_RS025

Template No.: CS\_TP\_BS016 Revision 6

Reference: CS\_WI\_BS005

Effective Date: 02Dec2019

Copyright © 2009, 2010, 2012, 2016, 2018, 2019 [REDACTED] All rights reserved. The contents of this document are confidential and proprietary to [REDACTED] Holdings Inc. and its subsidiaries. Unauthorized use, disclosure or reproduction is strictly prohibited.

## COVID-19 Statistical Analysis Plan

- Immunoglobulin M (IgM) (if data available);
- Serostatus (positive, negative, indeterminate) (if data available).

The following comorbidities, as captured on the Medical History page of the eCRF, will also be reported for this study:

- Any comorbidity, defined as having any of the comorbidities listed below;
- Diabetes;
- Heart Disease;
- Chronic Lung Disease;
- Chronic Liver Disease;
- Asthma;
- HIV;
- Tuberculosis;
- Alcohol Abuse;
- Drug Abuse.

Continuous demographic and other baseline characteristics will be summarized using descriptive statistics overall and by treatment group based on the SAF analysis set. For categorical demographic and other baseline characteristics, number and percentage of subjects in each category will be provided overall and by treatment group based on the SAF analysis set. No statistical testing will be carried out for demographic or other baseline characteristics.

Demographic, other baseline characteristics, and comorbidities data will be listed.

## 10.1. DERIVATIONS

BMI, in kg/m^2, will be calculated as follows:

- BMI (kg/ m^2) = weight (kg)/ [height (m)]

Document: \[REDACTED]\net\enterprise\Apps\sasdata\SASb\SAS\Atea\_Pharmaceuticals\AT-

527\527\Biostatistics\Documentation\SAP\AT-03A-001\_V1.0\_COVID\_SAP\_PA7.doc

Author: [REDACTED]

Version Number: V1.0

Version Date: 15Apr2021

Template No.: CS\_TP\_BS016 Revision 6

Reference: CS\_WI\_BS005

Effective Date: 02Dec2019

Copyright © 2009, 2010, 2012, 2016, 2018, 2019 [REDACTED] All rights reserved. The contents of this document are confidential and proprietary to [REDACTED] Holdings Inc. and its subsidiaries. Unauthorized use, disclosure or reproduction is strictly prohibited.

